2.2 Secondary objective(s)

[figure not shown]
Group 1 secondary objectives:

1. To evaluate the change from baseline 1 (Visit 1 of the Core study) in LS-BMD Z-score at Month 18 and 24 by core treatment group.
2. To evaluate the change from baseline 1 (Visit 1 of the Core study) in LS and total body BMC at Month 18 and 24 by core treatment group.
3. To evaluate the change from baseline 1 (Visit 1 of the Core study) in serum N-terminal propeptide type I collagen (P1NP), cross linked N-telopeptide (NTX), bone specific alkaline phosphatase (BSAP) and tartrate-resistant acid phosphatase isoform 5b (TRAP-5b) at Month 18 and 24 by core treatment group.
4. To evaluate the proportion of patients with new clinical vertebral fractures during the 12 month extension period by core treatment group.
5. To evaluate the proportion of patients with new morphometric vertebral fracture during the 12 month extension period by core treatment group.
6. To evaluate the change from baseline 1 (Visit 1 of the Core study) in pain using the Faces Pain Scale-Revised (FPS-R) at Month 15, 18, 21 and 24 by core treatment group.
7. To evaluate the change from baseline 1 (Visit 1 of the Core study) in 2nd metacarpal cortical width at month 24 by core treatment group.
8. To evaluate the change from baseline 1 (Visit 1 of the Core study) in bone age and 2nd metacarpal cortical width at month 24 by core treatment group.

Group 2 secondary objectives:

1. To evaluate the change from (Extension) baseline 2 (visit 8A) in LS- BMD Z-score at Month 6 and 12.
2. To evaluate the change from (Extension) baseline 2 (visit 8A) in LS and total body BMC at Month 6 and 12.

3. To evaluate the relative change from (Extension) baseline 2 in serum N-terminal propeptide type I collagen (P1NP), cross linked N-telopeptide (NTX), bone specific alkaline phosphatase (BSAP) and tartrate-resistant acid phosphatase isoform 5b (TRAP-5b) at Month 6 and 12.
4. To evaluate the proportion of patients with new clinical vertebral fractures during the 12 month period.
5. To evaluate the proportion of patients with new morphometric vertebral fracture during the 12 month period.
6. To evaluate the change from (Extension) baseline 2 in pain using the Faces Pain Scale-Revised (FPS-R) at Month 3, 6, 9 and 12.
7. To evaluate the change from (Extension) baseline 2 in bone age and 2nd metacarpal cortical width at Month 12.

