6.4.6 Bone age and metacarpal cortical width assessment

Left postero-anterior (PA) hand/wrist X-ray will be taken at the final visit of Core study (for Group 1) or Visit 8A-Screening visit for Group 2 and at Visit 15/EOS (Month 24) for both Groups to assess bone age. The change in 2nd metacarpal cortical width at Month 24 relative to the respective baseline will be calculated.

If a fracture of the left upper extremity precludes radiographic imaging, (or precluded this X-ray in the Core study for Group 1) then the right hand will be evaluated for this purpose. In this case, the right hand should be imaged at both Visit 8 and at Visit 15/EOS (Month 24). The information will be used in the assessment of bone density.

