6.4.8 Appropriateness of efficacy assessments

Fracture determination by X-ray is the standard endpoint for long-term studies in osteoporosis. However, in studies of 12 months duration, change in BMD has become an acceptable surrogate and has been shown to be a strong indicator of the efficacy of anti-resorptive therapies, including bisphosphonates such as ZOL. Bone marker assessments of change in BSAP, P1NP, TRAP-5b and NTX often parallel the change in BMD over the same time course. NTX and TRAP-5b measure bone resorption while BSAP and P1NP measure bone

formation. In the growing child, height and bone age also indicate the overall effectiveness of an intervention, but in this study, only trends may be observed over the 12 month period. Bisphosphonates are considered effective in managing bone pain, including fracture pain, and the FPS-R is a scale used to measure pain in children.

The efficacy measurements listed above are therefore expected to be appropriate for this study.

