## Statistical methods planned in the protocol and determination of sample size

### Statistical and analytical plans

This document describes the statistical methodology for analyses of efficacy and safety in Study CZOL446H2337E1. The purpose of this study is to extend the period of observation in patients who have completed one year of evaluation in the Core study (CZOL446H2337) to evaluate the long-term safety and efficacy of zoledronic acid in osteoporotic children or adolescents treated with glucocorticoids. To ensure adequate intake of calcium and vitamin D, all children enrolled in this study will be provided with conservative intervention (diet with or without supplements), regardless of their treatment assignment.

The primary objective of this study is to demonstrate that zoledronic acid given long-term, over an additional 12 months from the Core study (CZOL446H2337), is safe for the treatment of osteoporotic children treated with glucocorticoids.

The secondary objectives include:

1. To evaluate the change from core baseline in LS-BMD Z-score at Month 18 and 24 by core treatment group.
2. To evaluate the change from core baseline in LS and total body BMC at Month 18 and 24 by core treatment group.
3. To evaluate the change from core baseline in serum N-terminal propeptide type I collagen (PINP), cross linked N-telopeptide (NTX), bone specific alkaline phosphatase (BSAP) and tartrate-resistant acid phosphatase isoform 5b (TRAP-5b) at Month 18 and 24 by core treatment group.
4. To evaluate the proportion of patients with new clinical vertebral fractures during the 12 month extension period by core treatment group.
5. To evaluate the proportion of patients with new morphometric vertebral fracture during the 12 month extension period by core treatment group.
6. To evaluate the change from core baseline in pain using the Faces Pain Scale-Revised (FPS-R) at Month 15, 18, 21 and 24 by core treatment group.
7. To evaluate the change from core baseline in 2nd metacarpal cortical width at month 24 by core treatment group.
8. To evaluate the change from core baseline in bone age and 2nd metacarpal cortical width at month 24 by core treatment group.

Categorical data will be presented as frequencies and percentages. For continuous data, mean, standard deviation, median, minimum, and maximum will be presented.

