## Analysis for efficacy variables

If otherwise not specified, the efficacy data will be summarized and analyzed with respect to core baseline only and will be presented by the core treatment group and visit. The mean, median, standard deviations, and range of each variable and its change from baseline measured on a continuous scale, will be presented by core treatment group and visit. Number and percentage of patients will be presented for categorical variables by core treatment group and visit. All hypothesis tests will be evaluated at a 0.05 level of significance, and the p-values will be rounded to the 4th decimal place. Change from baseline at Month X is defined as value at Month X - value at baseline. Percentage change from baseline is defined as 100 times the change from baseline divided by the baseline value. Missing values will not be imputed or replaced.

The efficacy variables and their analysis methods are described below.

- **Percent change in lumbar spine areal BMD Z-score at Months 18 and 24 relative to baseline, zoledronic acid group vs. placebo**

The percent change in LS-BMD Z-score at Months 18 and 24 relative to core baseline between zoledronic acid and placebo (the core treatment groups) will be evaluated using an ANCOVA model with core treatment, pooled center, underlying condition treated with glucocorticoids and core baseline LS-BMD Z-score as explanatory variables and pooled centers as random effect.

From the model, core treatment difference in least squares means between zoledronic acid group vs. placebo group will be estimated and presented together with two-sided 95% CI and p-value. In the same table, the LS means and standard errors for percent change from baseline in LS-BMD Z-score at Month 18 and Month 24 will be presented for each core treatment group. Descriptive statistics will also be shown for baseline, Month 18 and Month 24 visits.

- **Change in lumbar spine and total body BMC at Months 18 and 24 relative to baseline, zoledronic acid group vs. placebo**

The change in BMC at the lumbar spine and total body at Months 18 and 24 relative to core baseline between zoledronic acid and placebo will be evaluated using an ANCOVA model with core treatment, pooled center, underlying condition treated with glucocorticoids and core baseline BMC as explanatory variables and pooled centers as random effect.

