The number and percentage of patients with new vertebral fractures and new morphometric vertebral fractures during the 12 month extension period will be presented by core treatment group. Between-treatment differences will be evaluated using Fisher's exact test. New vertebral fractures are defined as fractures of Genant grade 1 or higher that occur at lumbar or thoracic spine from first extension dose infusion to the end of the extension study. New morphometric vertebral fractures during the 12 month extension period is defined as a morphometric vertebral fracture present at Month 24 X-ray which is not present at extension baseline.

- **Change in 2nd metacarpal cortical width at Month 24 relative to baseline, zoledronic acid group vs. placebo**

The change in 2nd metacarpal cortical width at Month 24 relative to core baseline will be evaluated using an ANCOVA model with core treatment, pooled center, underlying condition treated with glucocorticoids and core baseline bone age as explanatory variables and pooled centers as random effect.

From the model, core treatment difference in least squares means between zoledronic acid group vs. placebo group will be estimated and presented together with two-sided 95% CI and p-value. In the same table, the LS means and standard errors for change from baseline in 2nd metacarpal cortical width at Month 24 will be presented for each core treatment group. Descriptive statistics will also be shown for baseline and Month 24 visits.

[figure not shown]
Above analysis will be carried out with respect to both baselines (core baseline as well as extension baseline).

[figure not shown]
- **Reduction in pain from baseline, zoledronic acid group vs. placebo**

[figure not shown]
Pain is assessed using Faces Pain Scale-Revised (FPS-R) at first infusion in the extension study (Visit 9), Month 15, 18, 21 and 24, which ranges from 0 (No Pain) to 10 (Very Much Pain). Details of FPS-R can be found in Appendix section “Faces Pain Scale” in the protocol.

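### Change in bone age is a secondary objective in both groups, but the readable analysis text uses it only as a covariate; separately, metacarpal change can compare opposite hands

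*Protocol*

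**What the plan says.** **Objectives.** Protocol Section 2.2 gives Group 1 objective 8 as change from Core Visit 1 "in bone age and 2nd metacarpal cortical width at month 24 by core treatment group". Group 2 objective 7 is change from the extension baseline "in bone age and 2nd metacarpal cortical width at Month 12". The SAP repeats the Group 1 objective under Statistical and analytical plans: "To evaluate the change from core baseline in bone age and" metacarpal width at Month 24.

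**Measurement.** Protocol Section 6.4.6 schedules a left hand/wrist film at baseline and again at "Visit 15/EOS (Month 24) for both Groups to assess bone age". The same film supplies metacarpal width. Section 6.4.8 says "In the growing child, height and bone age also indicate the overall effectiveness of an intervention", but the same sentence adds that this study can show only trends over its 12 months.

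**Analysis.** The SAP, under Analysis for efficacy variables, announces "The efficacy variables and their analysis methods are described below". In the readable items that follow, bone age appears once, in the metacarpal width model, which has "underlying condition treated with glucocorticoids and core baseline bone age as explanatory variables". Protocol Section 9.5.1.5 uses it the same way. The readable Other analyses lists in both documents include metacarpal width and not bone age.

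**Which hand.** If a left upper-limb fracture prevents the film, Section 6.4.6 moves to the other side: "In this case, the right hand should be imaged at both Visit 8 and at Visit 15/EOS (Month 24"). The SAP analyses metacarpal change from both the core and the extension baseline.

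**The concern.** Two separate problems sit in the same part of the plan.

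First, an objective stated for both groups has no named analysis in the readable text. If someone later fills the gap by tabulating raw change in bone age, the table will be hard to read. Bone age advances with the calendar in a growing child, so the raw figure contains elapsed time as well as any change in tempo, and the plan lets elapsed time vary between children.

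Second, the fallback to the right hand covers Visits 8 and 15 but not Core Visit 1, which is the baseline for the metacarpal objective. A child who changes hands after Visit 1 contributes a side-to-side difference to what is reported as change over time. Only children with a left upper-limb fracture can be affected.

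**Working it through.** The plan gives no power, effect size or standard deviation for either measure, so there is no figure of its own to reproduce. The check is a trace through the documents plus simple arithmetic on the intervals.

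**1. Where bone age appears**

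| Place | Role of bone age |
|---|---|
| Protocol 2.2, Group 1 objective 8 and Group 2 objective 7 | Outcome |
| SAP objectives, item 8 | Outcome |
| Protocol 6.4 and 6.4.6 | Assessment |
| Protocol 9.5.1.5 | Covariate for metacarpal width |
| SAP metacarpal width item | Covariate for metacarpal width |
| Other analyses, Protocol 9.5.1.10 and SAP | Not named in readable text |

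For Group 2, Protocol 9.5.1.5 offers summary statistics under the metacarpal heading only. The SAP defines no Group 2 analysis set: its FAS and SAF both require completion of the Core study.

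**2. Elapsed time between films**

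Group 1 inputs: Visit 8 closes the one-year Core study (taken as Month 12). Visit 9 may be up to 4 months after Visit 8 (Protocol 3.1). Visit 15 is 12 months after Visit 9 (Table 6-1).

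- Shortest: 12 + 0 + 12 = 24 months = 2.0 years.
- Longest: 12 + 4 + 12 = 28 months = 2.33 years.

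Group 2 inputs: the baseline film is at Visit 8A. Visit 9 should be about 28 days later and no more than 8 weeks (Table 6-2; Section 3.1 gives 30 days). Visit 15 is 365 days after Visit 9 (Appendix 7).

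- About 28 days: (28 + 365)/365 = 1.08 years.
- 8 weeks: (56 + 365)/365 = 1.15 years.

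**3. What raw change contains**

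Assume normal tempo means one year of bone age per calendar year. With no drug effect, raw change is then 2.0 to 2.3 years in Group 1 and about 1.1 to 1.15 years in Group 2.

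Let D = bone age minus chronological age on the film date. Then change in D = change in bone age − elapsed time.

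Take a raw gain of 2.0 years in Group 1:

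- Over 24 months: tempo 2.0/2.0 = 1.00; change in D = 0.
- Over 28 months: tempo 2.0/2.33 = 0.86; change in D = 2.0 − 2.33 = −0.33 years.

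The raw figure is the same; D separates the two cases.

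**4. Between Group 1 arms**

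At normal tempo, elapsed time adds the difference in mean interval between arms. That is 0 if the intervals match and at most 4/12 = 0.33 years if every child in one arm sat at 24 months and every child in the other at 28. Similar follow-up therefore removes most of it.

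**5. Skeletally mature patients**

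Group 1 admits patients up to 19 years (Protocol 4.1). If bone age no longer advances, change in D = 0 − 2.0 to 0 − 2.33, a fall of 2.0 to 2.3 years whatever the drug does. D needs a rule for these patients.

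**6. Which hand is filmed (Group 1, assuming a left-hand film at Visit 1 unless it was prevented)**

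| Left arm first unusable at | Visit 1 | Visit 8 | Visit 15 | Change from core baseline | Change from extension baseline |
|---|---|---|---|---|---|
| Visit 1 | Right | Right | Right | Same hand | Same hand |
| Visit 8 | Left | Right | Right | Right minus left | Same hand |
| Visit 15 | Left | Left | Right | Right minus left | Right minus left |

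In the last row the rule asks for a right-hand film at Visit 8 that can no longer be taken. The first row assumes the Core study used the same fallback. The rule also names Visit 8, whereas Group 2's baseline film is at Visit 8A. The SAP's baseline definitions do not mention the hand.

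**The case against.** A reader might infer that the objective has no analysis at all. The documents do not support that. Protocol numbering runs from 9.5.1.6 to 9.5.1.10 with redaction between, text is redacted after the Protocol's Other analyses list, and parts of the SAP are not shown. Absence can be asserted only for what is readable. Both documents also promise summary statistics for each continuous variable and its change from baseline, which could be taken to include bone age, and an objective to evaluate a change can be met descriptively. This stands. What remains is that the SAP names its efficacy variables one by one and, in readable text, bone age is not among them.

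A reader might also infer that raw change cannot show delayed maturation. It can, when set against a known interval: a gain well below elapsed time indicates delay. The weakness is that the interval varies and a raw table does not show it. Nor is the Group 1 between-arm comparison necessarily distorted, since elapsed time largely cancels there.

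Three further limits are fair. Section 6.4.8 itself expects only trends. Section 3.6 discusses linear growth and metaphyseal fracture without mentioning bone age, so it cannot be cited as requiring this measure. The films are not taken for bone age alone, because metacarpal width needs them too.

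On the hands, the case against is that the trigger is narrow, the Visit 1 hand depends on a Core protocol that is not available, and the extension-baseline analysis is same-hand when the fracture is present at Visit 8. All of that is correct. It limits the size of the problem but does not remove it.

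**Conclusion.** The point holds in a limited form. Bone age is a stated secondary objective in both groups, and its analysis is not specified in readable text beyond a generic descriptive clause. If raw change is what gets reported, Group 1 within-arm figures carry about 2.0 to 2.3 years of elapsed time and Group 2 figures about 1.1 years, assuming normal tempo and Visit 8 at Month 12. The Group 1 between-arm contrast is little affected if follow-up is similar.

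The metacarpal problem is real as the rules are written, assuming a left-hand film at Core Visit 1. It is confined to children whose left arm becomes unusable for imaging after Visit 1. Neither their number nor the typical left-right difference is given, so any bias cannot be computed; the number is probably small. Both matters should be settled in the SAP before database lock. Neither bears on the primary safety objective.

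**What to change.** Add to the SAP:

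- **Group 1:** change from core baseline to Month 24 in bone age minus chronological age on the X-ray date, summarised by core treatment group. Fit the ANCOVA already used for the other continuous endpoints, with the baseline value of that difference as covariate, and label it exploratory.
- **Group 2:** the same quantity from Visit 8A to Month 12, descriptive only, placed wherever Group 2 analyses are specified. The readable SAP has no Group 2 analysis set, and this addition does not repair that wider gap.
- **Skeletally mature patients:** define maturity at baseline in advance, and exclude these patients from the summary or list them separately.
- **Metacarpal width:** compute change only between films of the same hand, for each baseline separately. Otherwise set that change to missing and list the patient with the hand used at each visit.

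The cost is SAP wording and one extra table. No new film is needed, given that birth dates and X-ray dates are held. The downside is that a few metacarpal changes become missing, among children who have fractured.

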3.1 Study design

This study is a 1-year open-label extension to the CZOL446H2337 Core study. The study uses a single treatment arm (zoledronic acid); there will be no placebo or active control group. All patients will be osteoporotic children and adolescents receiving GC therapy of any duration within the 12 months preceding Baseline (Visit 1 of the Core study for Group 1; Visit 8A of this study for Group 2). All patients must manifest a LS-BMD Z-score of -0.5 or worse and have evidence of low impact/fragility fracture at either the Baseline of the Core Study (Group 1) or this study (Group 2).

Group 1: Patients who have received at least one dose of study drug and who have completed the Core study and who meet the inclusion/exclusion criteria for this Extension study will be eligible to enroll. The final visit of the Core study (Visit 8) will serve as the first (screening) visit for the Extension study. At Visit 8A, which may take place on the same day as Visit 8, patients will complete additional screening assessments for the Extension study. Patients will return at Visit 9 (which can also be on the same day as Visit 8 of the Core study) and all patients will receive zoledronic acid. The allowed window for Visit 9 is up to 10 months after Visit 5 (month 6) of the Core study (up to 4 months after Visit 8 of the Core study). Note that Visit 8 and Visit 9 can be combined if the patients or parents or legal guardians have provided informed consent to enter into the Extension study prior to Visit 8 and undergone the appropriate screening procedures as outlined in [Section 6](#). Central labs from Visit 8 will be utilized for the Extension Visit 9, provided the lab samples have been collected within 30 days prior to the Visit 9 infusion. Otherwise, the labs must be redrawn and the results reviewed for eligibility, prior to infusion at Visit 9. The DXA scans (hip, spine and distal femur) from Visit 8 will be used for the extension Visit 9 provided the DXAs have been obtained within 3 months of the Visit 9 infusion; otherwise, the DXA scans must be repeated at Visit 9.

Group 2: Children, male or female, 5 to 17 years of age who otherwise met the inclusion criteria for entry into the Core study but did not complete screening on the Core study because of clinically significant back pain due to vertebral fracture and the preexisting clinical care at the Investigator's site is to treat this type of patient with a bisphosphonate.

Visit 8 A will serve as the first (screening) visit for Group 2. Patients will return at Visit 9 and all patients will receive zoledronic acid. The allowed screening window between Visit 8 A and Visit 9 is 30 days. Central labs from Visit 8 A will be utilized for Visit 9, provided the lab samples have been collected within 30 days prior to the Visit 9 infusion. Otherwise, the labs must be redrawn and the results reviewed for eligibility, prior to infusion at Visit 9. The DXA scans (hip, spine and distal femur) and X-rays collected at Visit 8 A will be read centrally and if the child/adolescent is eligible, used for Baseline provided the DXAs have been obtained within 3 months of Visit 9; otherwise, the DXA scans must be repeated at Visit 9.

All Patients (Group 1 and Group 2) will receive two infusions of i.v. zoledronic acid (0.05 mg/kg) with an interval of 6 months at Visit 9 and at Visit 12.

Safety and efficacy will be assessed at 6 (Visit 12) and 12 months (Visit 15), with additional visits 10 days after each infusion to evaluate on renal and calcium (Visit 10 and 13) as well as

telephone visits to assess pain, adverse events [REDACTED] and concomitant medication at 3 (Telephone Visit 11) and 9 (Telephone Visit 14) months.

